Developing Innovative PTSD Treatment for Children: Reconsolidation of Traumatic Memories Protocol™ for Children (RTM-C Protocol)

Research Protocol for a Mixed-Methods Pilot Study

Sponsor, Implementers, and Partners

Lead organisation: Global Institute for Mental Health Innovations, Networking and Development (GlobalInMind).

Partners: Charitable Foundation Voices of Children (Ukraine) and Quresta, Inc. (USA).

Project team: [name] (PI/RTM Protocol™ Lead-Trainer), [name] (team member, co-trainer/RTM Protocol™ Professional), [name] (research assistant/RTM Protocol™ Coach), [name] (team member/RTM Protocol™ Coach).

Background and Rationale

Post-traumatic stress disorder (PTSD) in children is a serious mental health problem that can develop after exposure to traumatic events such as war, violence, displacement, accidents, loss of loved ones, or abuse. PTSD in children is associated with intrusive memories, nightmares, physiological hyperarousal, avoidance of reminders, irritability, concentration difficulties, and impairments in family life, schooling, and social relationships. Although evidence-based psychological treatments exist for adults, there remains a major gap in effective, developmentally appropriate, and scalable interventions for children.

The Reconsolidation of Traumatic Memories (RTM) Protocol™ is a brief, non-pharmacological intervention originally developed for adults with PTSD. It is based on cognitive and neurobiological models of memory reconsolidation and dissociation. The RTM Protocol™ uses imagery to help individuals safely reprocess traumatic memories through a series of dissociative and imaginative steps (e.g., replaying memories in black-and-white, running them backwards, speeding them up). This process reconsolidates the traumatic memory in a less distressing form, leading to a reduction in flashbacks, nightmares, and distress responses. The RTM Protocol™ in adults has demonstrated strong clinical effectiveness across several clinical trials, with high acceptability and minimal risk of re-traumatisation.

The children's version (RTM-C Protocol) has not yet been formally evaluated and is being adapted and piloted in Ukraine, with training and implementation pathways planned through 2028. This research protocol outlines the pilot effectiveness and feasibility study for the RTM-C Protocol

scheduled for September 2025 – February 2026 using standardised outcome measures and ethically robust consent/data-protection procedures.

Aims and Hypothesis

Primary aim: Evaluate change in post-traumatic stress symptoms among children receiving RTM-C Protocol.

Secondary aims: (1) Assess functional impairment change across key domains (relationships, leisure, learning, happiness). (2) Assess acceptability/feasibility of RTM-C delivery and the value of auxiliary tools (animated instructions; cardboard cinema models). Generate qualitative feedback from trained specialists to refine language, tools, and procedures.

The study hypotheses that the RTM-C Protocol will significantly reduce PTSD symptoms in children, with effects maintained at 1- and 6-month follow-ups, and that children, parents, and therapists will find the intervention safe, acceptable, and feasible.

Study Design

This pilot study involves a mixed-methods evaluation.

A single-arm pilot with approximately 40–48 children, each treated by one of 20–24 trained RTM Protocol specialists. Children will complete six RTM-C Protocol sessions (plus parental sessions and diagnostic follow-ups). Outcomes will be measured at baseline, post-treatment, 1 month, and 6 months after treatment. Qualitative feedback will also be collected from specialists through structured focus groups.

This is a non-randomized, single-arm interventional pilot study. All participants will receive the Reconsolidation of Traumatic Memories in Children (RTM-C). Following the parent session (for consent and orientation), children will complete six structured RTM-C sessions, followed by diagnostic assessments at 1 and 6 months. This pilot study uses an open-label design with no masking, as the intervention requires active therapist and child engagement. The primary purpose is treatment: to test whether RTM-C reduces post-traumatic stress symptoms and improves child functioning, while also assessing feasibility and acceptability among children, parents, and providers.

Participants

The pilot targets 40-48 children (20–24 providers \times 2 clients). This is adequate to estimate recruitment/retention, feasibility, and preliminary within-subject effect sizes (Cohen's d) to inform Stage-2/3 scaling and any future controlled trials.

Inclusion Criteria: (1) Age 6–14 years at enrolment. (2) PTSD symptoms present: CATS-2 (Parent) total ≥ 15 at screening. (3) Functional impact: impairment endorsed in ≥ 1 CATS-2 domain (relationships, leisure, learning, happiness). (4) Consent/assent: written parent/guardian consent and child assent obtained. (5) Availability: child and caregiver can attend parent session + 6 treatment sessions and complete 1- and 6-month follow-ups. (6) Language/comprehension: child can understand session instructions and participate in tasks (with supports as needed). (7) Therapist

check of readiness: during Session 1 practice, child demonstrates reliable break state (disengages from imagery, re-orient to present, maintains eye contact, relaxed affect).

Exclusion Criteria: (1) Acute comorbid mental disorder. (2) Concurrent trauma-focused psychotherapy planned or ongoing during the study period. (3) Inability to understand/follow instructions due to cognitive impairment or other reasons that preclude participation. (4) Medical/neurological condition or situational factors (e.g., inability to commit to visits) that, in the investigator's judgment, would make participation unsafe or compromise study integrity.

Intervention

The children's version of the RTM Protocol™ (RTM-C Protocol) retains the essential procedural components of the adult method but is carefully adapted to meet developmental needs. Adaptations include:

- Child-friendly language and explanations.
- The use of play-based and imaginative exercises.
- Animated instructional videos and a cardboard "cinema" and "skreen" models to guide children through visualisation steps.
- Additional therapist strategies for emotional support, grounding, and engagement.
- Structured parental involvement before, during and after treatment sessions.

Outcomes and Measures

Primary: CATS-2 total scores at baseline, post-treatment, 1- and 6-month follow-ups.
Secondary: Functional impairment, acceptability, feasibility, and provider focus groups.

The study uses the CATS-2 (Child and Adolescent Trauma Screen) as the primary outcome measure. Both child self-report and parent-report versions will be administered. The CATS-2 provides scores for PTSD symptoms and functional impairment in relationships, learning, leisure, and happiness. An additional focus group interview will assess acceptability and feasibility from providers. Data will be collected at baseline, post-treatment, and at 1- and 6-month follow-ups.

Procedures and Timeline

RTM-C Protocol administration involves six structured sessions with the child, preceded by a parent session and followed by diagnostic follow-ups (at 1 month and 6 months after treatment), with both children and parents, to assess sustained outcomes.

Each session lasts approximately 60 minutes and follows a detailed, structured protocol. Animated instructions and cardboard "cinema" and "skreen" models are used as supportive tools only when verbal instructions are insufficient. Therapists are trained to avoid unnecessary use of tools that could prolong the session or burden the child. Children are rewarded at the end of sessions with small positive reinforcements (stickers, drawings, short games) to enhance engagement.

1. Screening & parent session (consent, parent CATS-2).
2. Session 1 (child assent, baseline CATS-2).
3. Sessions 2–6 (RTM-C Protocol administrations).
5. Follow-ups at 1 and 6 months.

Additional Documents

- **Parent/guardian informed consent** (voluntary; withdrawal without consequences; anonymisation; data rights; optional items for publication use, follow-up, archiving).
- **Child assent** (age-appropriate language; confidentiality; right to stop; option to bring a trusted adult/toy).
- **Parent memo** (what RTM-C is; expected reactions; home and in-session support; FAQs; safety; session count).
- **Information notice on personal data processing** (lawful basis; anonymisation; storage; rights).

Data Management and Protection

All identifying information will be anonymised using codes. Personal data will be securely stored in locked cabinets and password-protected computers in Ukraine. Anonymised datasets will be transferred via secure, certified platforms. Only trained RTM specialists have access to identified data. Researchers analyse only anonymised data.

Individual participant data (IPD) will not be shared outside the therapists who will collect data. This decision is based on the high sensitivity of the data, which involves trauma histories and mental health information from children. Even with de-identification, the small sample size and the vulnerability of the population create a risk of re-identification. For these reasons, only anonymised data will be shared with researchers, and only aggregated results will be shared through publications and presentations.

Training and Fidelity

All providers are certified RTM specialists. They receive additional one-day training in the RTM-C Protocol. Fidelity is supported through the use of protocol texts, animations, and visual tools, and monitored by session checklists and coaching. Feedback from therapists on usability, language, and feasibility will be used to refine the protocol before larger rollout.

Statistical Analysis Plan

Mixed models for CATS-2 change. Secondary analysis of functional impairment. Qualitative thematic analysis of provider feedback.

Ethical and Safety Considerations

The RTM-C Protocol emphasises “stress-free recall.” Children are not asked to provide detailed verbal descriptions of traumatic events. The therapist interrupts immediately if distress arises and redirects the child’s focus to a safe, neutral task. Work with traumatic material proceeds only once the child has demonstrated the ability to switch states reliably during practice (clear disengagement from imagery, reorientation to the present, ability to make eye contact, relaxed affect). These safeguards minimise the risk of re-traumatisation.

- **Minimal distress procedures** (stop/ground on first signs of discomfort; stress-free recall; parent presence when helpful).
- **Voluntariness and withdrawal** at any time without adverse consequences.

- **Child safeguarding and referral** where risk is detected; exclusion of acute comorbidities or concurrent trauma-focused therapy.
- **Independent ethical review** prior to data collection.

Significance

If effective, the RTM-C Protocol will provide an innovative, scalable, and low-burden treatment for PTSD in children. It could address a major unmet need in child mental health, particularly in humanitarian and post-conflict contexts. The pilot study in Ukraine is a first step toward larger implementation and evaluation, and findings will contribute to global knowledge on child-appropriate trauma interventions.

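### Readiness shown in Session 1 is an inclusion criterion, so the pilot's retention and feasibility sample is selected on early success with the intervention under study

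*Protocol*

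**What the plan says.** The Inclusion Criteria end with item 7, a therapist "check of readiness: during Session 1 practice, child demonstrates reliable break state". Four markers define that state: leaving the imagery, returning to the present, eye contact and calm affect.

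Session 1 is a counted session. Procedures and Timeline states that "RTM-C Protocol administration involves six structured sessions with the child", and inclusion criterion 5 requires that "child and caregiver can attend parent session + 6 treatment sessions". The numbered steps put screening and the parent session first, without a readiness check, and then "Session 1 (child assent, baseline CATS-2"). Step 3 covers Sessions 2 to 6 and is the only step labelled as RTM-C administration.

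Ethical and Safety Considerations gives the same check, with the same markers, as a safety gate: "Work with traumatic material proceeds only once the child has demonstrated the ability to switch states reliably during practice". That section does not tie the check to Session 1 and says nothing about eligibility.

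On purpose, Participants says of the 40–48 children: "This is adequate to estimate recruitment/retention, feasibility, and preliminary within-subject effect sizes". Study Design adds that the trial tests efficacy "while also assessing feasibility and acceptability among children, parents, and providers". Background and Rationale says that the child version "has not yet been formally evaluated and is being adapted and piloted in Ukraine".

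**The concern.** An inclusion criterion normally describes a child before the intervention begins. Item 7 describes how the child responds to the opening part of the intervention. Read as written, a child who assents, starts the first of the six sessions and cannot show a reliable break state was never eligible. The child does not count as a participant who could not continue.

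In a trial of an established treatment this might be a reasonable run-in. Here, whether children aged 6–14 can reach the break state in one session is part of what a feasibility pilot should find out. One marker is calm affect, so a child who stays distressed in practice also fails. Those children bear on retention, feasibility, acceptability and safety, and the rule as written removes them from the eligible sample. Figures meant to inform the next stages would then describe only children who succeeded early.

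**Working it through.** **Inputs from the protocol.** Target 40–48 children, from 20–24 providers with two clients each (Participants). Six child sessions (Study Design; Procedures and Timeline; inclusion criterion 5). No non-readiness rate, dropout rate or retention target is given.

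**Stated figure.** 20 × 2 = 40 and 24 × 2 = 48, so the target reproduces.

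**Is Session 1 one of the six?** Sessions 2 to 6 are five sessions, and 5 + 1 = 6. The count is reached only by including Session 1.

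**When can item 7 be met?** Only during Session 1 practice. The earlier screening step contains consent and the parent CATS-2, with no practice.

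**Effect on retention.** Let f be the share of starters not ready, r the retention of ready children and s the retention of non-ready children.

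- Non-ready children ineligible: retention = r.
- Every starter counted: retention = r(1 − f) + s·f.
- Overstatement = r − [r(1 − f) + s·f] = (r − s)·f.

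All values of r, f and s below are assumptions. At r = 90%, in percentage points:

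| f | s = 0 | s = 50% | s = 90% |
|---|---|---|---|
| 0% | 0 | 0 | 0 |
| 5% | 4.5 | 2 | 0 |
| 10% | 9 | 4 | 0 |
| 20% | 18 | 8 | 0 |

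The s = 0 column is the upper bound for each f at this r. If r runs from 80% to 100%, the upper bounds are 4–5, 8–10 and 16–20 points at f = 5%, 10% and 20%.

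**Per child.** With s = 0 and r = 90%, each non-ready child moves retention by at most 0.90/40 = 2.25 points (n = 40) or 0.90/48 = 1.875 points (n = 48).

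**Check in whole children (s = 0, f and later dropout both about 10%).** Of 40 starters, 4 are not ready and 4 of the other 36 drop out, leaving 32. Counting all starters gives 32/40 = 80.0% (Wilson 95% interval 65.2–89.5%). Counting only ready children gives 32/36 = 88.9% (74.7–95.6%). The gap is 8.9 points. Of 48 starters, with 5 not ready and 4 later dropouts, 39/48 = 81.3% compares with 39/43 = 90.7%. The gap is 9.4 points.

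The first interval is 89.5 − 65.2 = 24.3 points wide, so the gap is smaller than the sampling uncertainty. Unlike sampling error, it runs in one direction whenever s is below r.

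**The case against.** The best counter-reading is that Session 1 is in effect a run-in. Only Sessions 2–6 are labelled as administrations, and child assent, itself required by criterion 4, is obtained in Session 1. Eligibility therefore cannot be complete before that session on any reading. This stands as a real ambiguity, but it does not settle the matter: the protocol declares no run-in, and criterion 5 calls all six sessions treatment.

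It can also be said that denominators belong in an SAP, which is not shown. That is right for denominators alone, and their absence is not the point here. Eligibility is fixed in the protocol, and an SAP could not count these children as enrolled without overriding item 7.

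The safety purpose is sound. Ethical and Safety Considerations already secures it without making readiness an eligibility rule.

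Feasibility is also informed by provider focus groups, where therapists may mention children who were not ready, and such children could be reported as screen failures. Neither route puts them in a retention figure.

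A reader might infer more than the text supports:

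- **That the protocol says non-ready children are dropped from the estimates.** It does not. This follows from applying the inclusion rule.
- **That item 7 contradicts the ethics section.** The two differ in wording. The ethics section does not say that a child may keep practising in later sessions.
- **That a failing child always has a baseline score.** The order of CATS-2 and practice within Session 1 is not stated.
- **That retention will be overstated by 9 or 18 points.** Those figures need an assumed f and zero retention of non-ready children.

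**Conclusion.** The concern holds in a limited form. Item 7 is an eligibility rule that can be met only inside a session the protocol counts as treatment, so it selects the retention, feasibility and acceptability sample on early success with the intervention. The run-in reading keeps confidence at medium.

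The size cannot be determined from the protocol. It is (r − s)·f, with none of the three terms given, and may be nil. It is worth correcting because the bias falls on quantities the pilot says it can estimate, and because correction is cheap.

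**What to change.** Remove item 7 from the inclusion list and keep readiness as the gate to trauma work already stated under Ethical and Safety Considerations. Define enrolment as assent plus baseline CATS-2, both completed before the practice. Count every enrolled child in the retention, feasibility and safety denominators, and report the number not ready as a feasibility result.

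If the sponsor prefers to keep item 7 as an eligibility criterion, declare Session 1 a run-in, report how many children failed it, and limit conclusions to those who passed.

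The cost is protocol wording plus one ready/not-ready entry per child on the session checklists already planned. No safeguard is lost and no visit or assessment time point is added. There are three downsides. Reported retention may be lower. Somewhat fewer of the 40–48 may be fully treated, which leaves less information for the within-subject effect size. Non-ready children who stay in would be due the CATS-2 follow-ups already scheduled, so those assessments would have to be carried out for them.
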